8.2.8 Safety Analyses

No safety analyses planned.

PFIZER CONFIDENTIAL

8.2.9 Summary of Analyses

Outcome	Analysis Set	Supports Protocol Objective Number	Subgroups	Statistical Method	Missing Data
Summary of age at initiation of palbociclib	Full Analysis set	Primary Objective	Overall and treatment Line	Calculated by subtracting Date of palbociclib initiation from Date of Birth. Summary statistics calculated (incl. Mean/Median/SD/IQR/Range)	Day of birth assumed to be the 15 th . If month is missing, birthday assumed to be 1 st July. Otherwise excluded.
Distributions of categorical, binary, and ordinal demographical and clinical characteristics	Full Analysis set	Primary Objective	Overall and treatment Line	Frequency tables and percentages	Excluded
Summary measures of MBC statistics	Full Analysis set	Primary Objective	Overall and Treatment Line	Frequency tables and percentages Summary statistics for Ki67 proliferation index (incl. Mean/Median/SD/IQR/Range)	Excluded
Duration of MBC at palbociclib initiation	Full Analysis set	Primary Objective	Overall and Treatment Line	Calculated by subtracting Date of palbociclib initiation from Date of MBC diagnosis. Summary statistics calculated (incl. Mean/Median/SD/IQR/Range)	Standard imputation for dates (section 7), otherwise exclude.
Treatment for MBC diagnosis prior to palbociclib initiation	Full Analysis set	Primary Objective	Overall and Treatment Line	Frequency tables and percentages	Excluded
Summaries of comorbidities and Charlson comorbidity index of patients at palbociclib initiation	Full Analysis set	Primary Objective	Overall and Treatment Line	Frequency tables and percentages for each comorbidity type Summary statistics calculated (incl. Mean/Median/SD/IQR/Range) for Charlson comorbidity index	Excluded
Palbociclib prescribed as on or off-label	Full Analysis set	Primary Objective	Overall and Treatment Line	Frequency tables and percentages	Excluded
Summary measures of palbociclib treatment patterns	Full Analysis set	Secondary Objective 1	Overall and Treatment Line	Frequency tables and percentages for proportions and categorical variables such as proportion of patients with dose reductions or discontinuation and reasons for discontinuation Summary statistics calculated (incl.	Excluded

PFIZER CONFIDENTIAL

				Mean/Median/SD/IQR/Range) for doses, time to dose reduction and discontinuation and length of treatment	
Describing treatment patterns 1,2 and 3 years after palbociclib initiation	Full Analysis set	Secondary Objective 1	Overall and Treatment Line	Frequency tables and percentages for proportions of patients completing a 28-day cycle, co-administered letrozole and fulvestrant at palbociclib initiation. Summary statistics calculated (incl. Mean/Median/SD/IQR/Range) for number of completed 28-day cycles	Excluded
Proportion of patients free from disease progression	Full Analysis set	Secondary Objective 2	Overall and Treatment Line	Frequency tables and percentages	Excluded
Proportion of patients alive	Full Analysis set	Secondary Objective 2	Overall and Treatment Line	Frequency tables and percentages	Excluded
Proportion of patients achieving PR/CR/with stable disease	Full Analysis set	Secondary Objective 2	Overall and Treatment Line	Frequency tables and percentages	Excluded
Median PFS	Full Analysis set	Secondary Objective 2	Overall and Treatment Line	Kaplan-Meier analysis, median PFS measured as being time from the date of palbociclib initiation to the date of first document disease progression or death. 95% confidence intervals calculated for median.	Standard imputation for dates (section 7), otherwise exclude.
Median OS	Full Analysis set	Secondary Objective 2	Overall and Treatment Line	Kaplan-Meier analysis, median OS measured as being time from the date of palbociclib initiation to the date of death. 95% confidence intervals calculated for median.	Standard imputation for dates (section 7), otherwise exclude.
Median time to best overall response (CR or PR)	Full Analysis set	Secondary Objective 2	Overall and Treatment Line	Kaplan-Meier analysis, time to first best overall response (partial/complete response) measured as being time from the date of palbociclib initiation to the date of first response. 95% confidence intervals calculated for median.	Standard imputation for dates (section 7), otherwise exclude.
Swimmer plots	Full Analysis set	Secondary Objective 2	Overall and Treatment Line	Swimmer plots used to represent patient response (CR / PR/ stable disease / progressive disease) to treatment for patients responding to treatment (CR or PR).	
Duration of response (PR/CR)	Patients enrolled achieving PR/CR	Secondary objective 2	Overall and Treatment Line	Kaplan-Meier analysis, median duration of response measured as being time from the	Standard imputation for dates (section 7),

PFIZER CONFIDENTIAL

	during follow-up in Full Analysis set			date of CR/PR to documented disease progression or death. 95% confidence intervals calculated for median.	otherwise exclude.
Proportion of patients experiencing neutropenia and febrile neutropenia for first year post-observation period	Full Analysis set	Secondary objective 3	Overall and by grade of neutropenia. Treatment Line	Summary statistics calculated (incl. Mean/Median/SD/IQR/Range) and frequency and percentages of proportions of patients with neutropenia and febrile neutropenia.	Excluded
Proportion and summary measures of patients experiencing gastro-intestinal toxicity during first year observation period	Full Analysis set	Secondary objective 4	Overall and Treatment Line	Summary statistics calculated (incl. Mean/Median/SD/IQR/Range) and frequency and percentages of proportions of patients with experiencing gastro-intestinal toxicity including diarrhoea, nausea, and vomiting.	Excluded
Summary measures of full blood counts in the first year of initiation	Full Analysis set	Secondary objective 5	Overall and Treatment Line	Summary statistics calculated (incl. Mean/Median/SD/IQR/Range) of haemoglobin, white cell counts, absolute neutrophil counts, and platelet counts. The mean, median, minimum, and maximum reading will be used where multiple tests are taken within the study period.	Excluded
Summary measures of liver function tests in the first year following initiation of palbociclib	Full Analysis set	Secondary objective 5	Overall and Treatment Line	Summary statistics calculated (incl. Mean/Median/SD/IQR/Range) aspartate transaminase, alanine transaminase and alkaline phosphatase. The mean, median, minimum, and maximum reading will be used where multiple tests are taken within the study period.	Excluded
Summary measures of bone profile in the first year of initiation	Full Analysis set	Secondary objective 5	Overall and Treatment Line	Summary statistics calculated (incl. Mean/Median/SD/IQR/Range) of calcium and phosphate. The mean, median, minimum, and maximum reading will be used where multiple tests are taken within the study period.	Excluded
Summary measures of radiological indicators in the first year of initiation	Full Analysis set	Secondary objective 5	Overall and Treatment Line	Frequency and percentages for proportions of patients with stable and progressive disease or CR or PR. Where there is more than one test, the first, most common and most favourable test results will be used.	Excluded
Summary measures of hospital admissions for each	Full Analysis set	Secondary objective 6	Overall and Treatment Line	Frequency and percentages of inpatient, outpatient and emergency department visits	Excluded

PFIZER CONFIDENTIAL

line of therapy				and summary measurements of visits per patient (incl. Mean/Median/SD/IQR/Range) and lengths of inpatient stay	
Summary of phone calls from patient to Cancer National Services	Full Analysis set	Secondary objective 6	Overall and Treatment Line	Frequency and percentages for phone calls and reasons for visit	Excluded
Summary of phone calls from patient to Acute Oncology Services	Full Analysis set	Secondary objective 6	Overall and Treatment Line	Frequency and percentages for phone calls, reasons for visit and contact types	Excluded

PFIZER CONFIDENTIAL

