7 HANDLING OF MISSING VALUES

Where dates are ambiguous because of missing day and/or months, standard imputation will be applied: where day is missing the 15th of the month will be assumed; where both day and month are missing the 1st of July will be assumed unless data collected is in 2017 (year of initiation of IPP) in which case the 15th of August will be assumed (midpoint as IPP was initiated in April 2017). The 15th of August will only be used for missing dates that are related to the IPP program, e.g., start date of palbociclib cycle. Where other types of data are missing from the original medical record, the affected analyses will be conducted using only the results of those patients with data available and the number included in each analysis will be stated. The percentage of data missing will be reported for each study variable. The calculation of percentages will not contain the missing categories. Counts of missing observations will be presented in a separate category.

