8.2 STATISTICAL ANALYSES

Definitions will be implemented as in section 8.1.3. Patients who are known to be alive at the date of data collection (1-year for interim report and 3-year for full study report) will be censored at the date of data collection, and patients who are lost to follow-up will be censored on the date they were last known to be alive (e.g., date of last recorded hospital visit). Patients who are alive and free from disease progression at the date of data collection and those lost to follow-up will be censored on the date they were last known not to have disease progression (i.e., the date of last documented response assessment). Patients remaining in CR or PR at the end of the post-initiation observation period or lost to follow-up will be censored on the date CR or PR was last documented.

[figure not shown]
[figure not shown]
Note: Some analyses that were originally proposed were not conducted as per the decisions of the CI and Pfizer team, these have been kept in this section as a record.

8.2.1 Primary Objective: To describe patient demographic and clinical characteristics at initiation of palbociclib.

Proposed: Age, duration of MBC prior to palbociclib (calculated by subtracting the date of initial BC diagnosis from the date of palbociclib initiation), number of lymph nodes involved, tumour size at initial disease diagnosis and Ki67 values will be summarised as quantitative variables (see section 8.1.1) using measures of central tendency (mean and median) and dispersion (standard deviation, interquartile range [IQR] and range) will be calculated. All other variables analysed as part of the primary endpoint, whether categorical or binary, will be presented as frequencies and percentages.

Actual: Age was presented as both a quantitative variable as per section 8.1.1 and as a categorical variable (Categories: Less than 40 years old, between 40 and 50 years old,

PFIZER CONFIDENTIAL

[figure not shown]

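### SAP table 8.2.9 drops patients with a known but undated progression or death from PFS, OS and duration of response, so this exclusion depends on the outcome

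*SAP*

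**What the plan says.** SAP table 8.2.9 (Summary of Analyses) gives the same missing-data entry for median PFS, median OS and duration of response: "Standard imputation for dates (section 7), otherwise exclude".

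SAP section 7 defines the standard imputation. For a partial date, "where day is missing the 15th of the month will be assumed"; and "where both day and month are missing the 1st of July will be assumed unless data collected is in 2017", when 15 August is used for dates related to the access programme. Only a date without a year therefore remains beyond imputation. For other types of missing data the section uses available cases and states the number analysed. It adds: "The percentage of data missing will be reported for each study variable".

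SAP section 8.2 sets the censoring rules. Patients known to be alive are censored at data collection. For loss to follow-up, "patients who are lost to follow-up will be censored on the date they were last known to be alive". For PFS, event-free and lost patients are censored at the last documented response assessment. Patients still in response are censored when the response was last documented. No rule covers a patient known to have died or progressed on an unknown date, so the table's exclusion governs that patient.

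**The concern.** A progression or death date can be missing only in a patient who had that event. Excluding such a patient removes a known event from the event count and the patient from the risk set. A surviving or progression-free patient cannot be excluded for that reason. For event dates, then, the rule selects on the outcome.

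The asymmetry is clearest for OS. Living patients are censored at a date the study itself records, and lost patients fall back on the last hospital visit. A missing censoring date is unlikely there, whereas a missing death date removes only deaths.

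PFS, OS and duration of response are the main effectiveness results of a chart-review study. Protocol section 9.9 itself says that interpretation depends on how complete the records are. Reporting the number analysed shows the loss but does not correct the estimate, and no sensitivity analysis is planned for it.

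**Working it through.** The plan states no figure to reproduce: it gives no rate of undated events and no target survival. The figures below are illustrations.

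**Inputs**
- Median PFS of 24.8 months: the palbociclib arm of the first-line phase III trial cited in protocol section 7. It is used as an assumption, with exponential times.
- Cut at 24 months (SAP sections 5.1 and 8.1) or 36 months (still mentioned in SAP section 8.2).
- About 200 patients (SAP section 2.1).
- m, the share of events that are undated: assumed, 1% to 20%.

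**Formula.** Let F(t) be the true event probability by time t and p = F(T) at the cut T. If undated events are a random share m, nobody else is lost and these patients are excluded, the reported survival is

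S*(t) = 1 − (1 − m)F(t)/(1 − m·p), which at t = T reduces to (1 − p)/(1 − m·p).

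**24-month PFS.** Hazard = ln 2/24.8 = 0.02795 per month, so p = 1 − exp(−0.02795 × 24) = 0.4887 and the true value is 51.1%. For example, m = 10% gives 0.5113/(1 − 0.04887) = 53.8%.

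**Median with a 36-month cut.** Here p = 0.6344. The reported median is the time at which F = 0.5(1 − m·p)/(1 − m). For m = 10%, F = 0.5 × 0.9366/0.9 = 0.5203, and the time is −ln(0.4797)/0.02795 = 26.3 months.

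| m | excluded of 200 (24-month cut) | 24-month PFS (true 51.1%) | median, 36-month cut (true 24.8) |
|---|---|---|---|
| 1% | 1 | 51.4% | 24.9 |
| 2% | 2 | 51.6% | 25.1 |
| 5% | 5 | 52.4% | 25.5 |
| 10% | 10 | 53.8% | 26.3 |
| 20% | 20 | 56.7% | 28.2 |

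**OS.** With an assumed 2-year survival of 80%, the same formula gives 0.80/(1 − 0.20m): 80.3% at m = 2%, 80.8% at 5% and 81.6% at 10%. For an assumed 70% or 90%, m = 10% gives 72.2% or 90.9%.

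**Does timing matter?** Under a 24-month cut with complete follow-up, excluding d of E events among N patients gives (N − E)/(N − d), which exceeds (N − E)/N whenever the excluded events occurred. Suppose 20% of the events in one period are undated, with F(8) = 0.2004, F(16) = 0.3606 and F(24) = 0.4887:
- months 0 to 8: 0.5113/(1 − 0.0401) = 53.3%
- months 8 to 16: 0.5113/(1 − 0.0320) = 52.8%
- months 16 to 24: 0.5113/(1 − 0.0256) = 52.5%

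In the last case the 12-month estimate falls, from 71.5% to 1 − 0.2849/(1 − 0.0256) = 70.8%.

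**Is the direction fixed?** A Kaplan-Meier simulation used 400,000 patients, a median of 24.8 months and staggered censoring up to 36 months. The resulting medians were:
- 20% of events before month 12 excluded: 26.9
- 20% of events after month 24 excluded: 24.0 (24-month PFS 50.0%)
- 10% of censored patients excluded: 23.3
- 10% of all patients excluded: 24.7

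**Does keeping the events help?** In the same simulation with 10% of events undated at random, exclusion gave a median of 26.5. Keeping these patients as events, with dates spread over their own follow-up, gave 25.1. The bounds were 24.3 (all at index) and 27.8 (all at the end of follow-up). A separate simulation with 3-monthly assessments, data collection at 36 months and a true median of about 24.7 compared exclusion with midpoint dating: 25.0 and 25.0 at 2% undated, 25.4 and 25.3 at 5%, 26.2 and 25.6 at 10%.

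**The case against.** A reader might infer that the rule always overstates survival and never removes an event-free patient. The documents do not support that. The clause covers every date the analysis needs. A progression-free patient with no dated response assessment has no PFS censoring date and can be excluded too, which pulls PFS down. A missing index date is roughly neutral. Late undated events can lower the median and earlier estimates.

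It is also tempting to cite progression mentioned only in a later clinic letter. The protocol's PFS definition (section 9.3) would count it, but SAP section 6 restricts progression to the radiological assessment section of the eCRF, where each assessment is collected with its date. Such a case may not be a PFS event under the SAP at all.

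The trigger is narrow: the year must be unknown within at most three years of follow-up. The eCRF has consistency checks, and missing items are queried against source records (protocol sections 9.6 and 9.8). With 200 patients, the standard error of a 51% proportion is about √(0.511 × 0.489/200) = 3.5 points, so even the 2.7-point shift at 10% undated lies within one standard error. The study is descriptive and tests no hypothesis.

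All of this stands, and it limits the likely size. It does not justify the rule. Queries reduce the number of undated events but do not say what to do with those that remain, and a systematic error is not excused by being smaller than the random one.

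**Conclusion.** The point holds in a limited form. For a missing event date, table 8.2.9 prescribes an exclusion that depends on the outcome, and nothing else in the SAP overrides it. It overstates survival if event dates are missing at random in time or mainly for early events. It overstates 24-month survival whatever the timing within the window, provided the cut is at 24 months, follow-up is complete and only event patients are excluded. Across all reasons for exclusion, the net direction is unknown.

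On the assumptions above, the effect on 24-month PFS is about 0.3 to 0.5 points if 1% to 2% of events are undated, 1.3 points at 5% and 2.7 points at 10%. The documents give no rate, and data queries should keep it low. This is a rule that should be replaced because a better one is cheap; it does not threaten the study's conclusions as planned.

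The SAP also leaves open whether a patient with undated progression but a dated death counts as a PFS event at death.

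**What to change.** In table 8.2.9, for PFS, OS and duration of response:

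1. Limit "otherwise exclude" to a missing index date or, for duration of response, a missing response start date.
2. Keep a patient with a known but undated event as an event, interval-censored between the last dated record showing the patient event-free and the date of data collection (or the dated death, for undated progression).
3. Use the midpoint or an interval-censored estimate, with the earliest and latest possible dates as sensitivity bounds.
4. Censor an event-free patient with no dated response assessment at the index date instead of excluding the patient. This keeps the patient in the count but does not move the Kaplan-Meier curve, since a patient censored at time zero is never at risk.
5. Report the numbers affected separately for missing event, index and censoring dates. If no event is undated, say so.

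The cost is a short change to the SAP text and one sensitivity run. No new data are needed: assessments, cycles, laboratory tests and data collection are already dated in the eCRF. However, death and last clinic visit appear together in one entry of the variable list, so the last-alive date of a deceased patient may have to come from those other records. The imputed dates are approximate for a few patients, and the midpoint removes only part of the bias in the median.

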Definitions will be implemented as described in section 9.3 Variables. Patients who are known to be alive at the date of data collection (1-year for interim report and 3-year for full study report) will be censored at the date of data collection, and patients who are lost to follow-up will be censored on the date they were last known to be alive (e.g. date of last recorded hospital visit). Patients who are alive and free from disease progression at the date of data collection and those lost to follow-up will be censored on the date they were last known not to have disease progression (i.e. the date of last documented response assessment). Patients remaining in CR or PR at the end of the post-initiation observation period or lost to follow-up will be censored on the date CR or PR was last documented.

For the estimation of the proportion of patients alive, and free from disease progression, the denominator will be all patients known to be alive at the selected time-points (1 years, 2 years and 3 years). For the estimation of the proportion of patients achieving PR, CR and with stable disease at the selected time-points (1 years, 2 years and 3 years), the denominator will be all patients with at least one assessment of response (CR / PR / no response or stable disease / progressive disease) in the past year. Estimation of time to achieving best overall response and duration of response; and representation using swimmer plots will be performed in patients who respond (achieve CR or PR during follow-up) only.

Median PFS, OS, time to achieving best overall response, time to palbociclib dose modification and time to palbociclib discontinuation, and corresponding 95% CIs, will be estimated using Kaplan-Meier curves. Assessments of response (CR / PR / no response or stable disease / progressive disease) in patients responding to treatment (achieving CR or PR following initiation of palbociclib) will be represented using “swimmer plots”.

All percentages will be reported to the nearest whole number; therefore, in reporting study results in tables, figures and associated text, percentages may not add up to 100% due to rounding.

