5.1 FULL ANALYSIS SET

The full analysis set will be comprised of medical records extracted for the purpose of the study from all eligible patients who are enrolled into the study (either deceased with access to their medical records via their direct care team or living and having provided written informed consent to access of their medical records as part of the study). Analysis will be conducted on the 2-year follow-up data.

PFIZER CONFIDENTIAL

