- Summary measures of bone profile in the first 6 months following initiation:
 - Calcium.
 - Phosphate.
- Summary measures of urea and electrolytes in the first 6 months following initiation:
 - Creatinine
 - Potassium
 - Sodium
 - Urea
- Summary measures of radiological indicators in the first 6 months following initiation including the proportion of patients with:
 - Stable disease.
 - Progressive disease.
 - CR or PR.

Secondary Objective 6: To describe BC-related healthcare resource utilisation during the first year following palbociclib initiation.

- Summary measures of hospital admissions for each line of therapy, including:
 - Proportion of patients with at least one inpatient admission recorded
 - Inpatient admissions per patient.
 - Elective or non-elective.
 - Reasons for admission (including day cases).
 - Length of stay per inpatient admission.
 - Proportion of patients with at least one outpatient visit recorded
 - Outpatient visits per patient.
 - Reason for outpatient visit
 - Type of HCP seen during outpatient visits
- Proportion of patients with at least one interaction with CNS
- Number of CNS interactions per patient
- Type of CNS interaction
- Reason for CNS interaction
- Proportion of patients with at least one interaction with AOS
- Number of AOS interactions per patient
- Type of AOS interaction
- Reason for AOS interaction

For the estimation of endpoints, *the following definitions will be implemented. PFS will be defined as the time from the date of palbociclib initiation to the date of first documented disease progression (as documented in the radiological assessment section of the eCRF) or death. OS will be defined as the time from the date of palbociclib initiation until death from any cause. Time to achieving best overall response will be defined in patients who respond to treatment as the time from the date of palbociclib initiation until*

PFIZER CONFIDENTIAL

achievement of the best overall response: CR, or PR if CR is not achieved during follow-up. Duration of response will be defined as the time from the date CR or PR was first documented (whichever is recorded first) to the date of first documented disease progression or death from any cause (whichever occurs first).

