prescribed treatment in the 1st, 2nd, and 3rd line after palbociclib discontinuation was presented as a categoric variable as per section 8.1.2. Dose, duration of subsequent treatments and number of completed 28-day cycles per patient were presented as quantitative variables as per section 8.1.1. Number of completed 28-day cycles (categories: 1-6 cycles, 7-12 cycles, 13-18 cycles, 19-24 cycles, 25-27 cycles and No completed cycles) and the proportion of patients co-administered letrozole or fulvestrant were presented as categoric variables as per section 8.1.2. All other endpoints were evaluated as proposed.

8.2.3 Secondary Objective 2: To describe overall survival and progression-free survival, response (CR, PR), stable disease. This includes estimating the proportion of patients achieving those endpoints at 1 and 2 following palbociclib initiation: median survival, time to response and duration of response. In patients who respond to treatment, to describe PR and CR using “swimmer plots”.

Proposed: For the estimation of the proportion of patients alive, and free from disease progression, the denominator will be all patients known to be alive at the selected time-points (e.g., 1 years, 2 years, and 3 years). For the estimation of the proportion of patients achieving PR, CR and with stable disease at the selected time-points (1 years and 2 years), the denominator will be all patients with at least one assessment of response (CR / PR / no response or stable disease / progressive disease) in the past year.

[figure not shown]
Actual: Proportion of patients free from disease progression, are alive, achieved PR, CR or stable disease were analysed separately at the 2-year timepoint only. Length of follow-up, and time to best response and first response were presented as quantitative variables as per section 8.1.1. Best response to palbociclib, overall and by de novo and relapse status was treated as a categoric variable and analysed according to section 8.1.2.

8.2.4 Secondary Objective 3: To describe the occurrence of neutropenia during the first-year post-initiation observation period.

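### The SAP 8.2.9 row for time to best overall response stops the clock at first response and is not limited to responders, contradicting SAP section 6 and the protocol

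*SAP*

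**What the plan says.** The SAP 8.2.9 row is headed "Median time to best overall response (CR or PR"). Its analysis set is "Full Analysis set", and its method is Kaplan-Meier. The row then fixes the start and end of the interval, which is "measured as being time from the date of palbociclib initiation to the date of first response". SAP 5.1 builds the Full Analysis Set from records "from all eligible patients who are enrolled into the study", so it includes patients who never respond.

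SAP section 6 defines the endpoint differently. It applies to patients who respond, and runs from palbociclib initiation to "achievement of the best overall response: CR, or PR if CR is not achieved during follow-up". Protocol 9.3 carries the same definition. Protocol 9.7 adds: "Estimation of time to achieving best overall response and duration of response; and representation using swimmer plots will be performed in patients who respond", and closes that sentence by confining it to those with CR or PR.

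SAP section 6 also lists time to best response and time to first response as separate endpoints, and promises a median with 95% CI for time to best overall response. The account of what was actually done in SAP 8.2.3 says "time to best response and first response were presented as quantitative variables as per section 8.1.1". It gives neither the event date nor the population.

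**The concern.** One named endpoint has two specifications inside the same SAP. They differ on when the clock stops and on who is counted.

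A programmer working from the table would report time to first response under the label of time to best response. The two endpoints that section 6 keeps apart would then carry the same numbers. If the analysis-set cell were also taken at face value, patients who never respond would enter the risk set, and the median would describe the whole cohort instead of responders.

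The figure at stake is one readers may set beside other palbociclib studies, so its meaning should not depend on which SAP page was used.

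**Working it through.** The documents state no response rate, CR rate or expected median for this endpoint, so there is no planned figure to reproduce. The check is a comparison of texts, followed by illustrations on stated assumptions.

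**1. The specifications side by side**

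| Place | Population | Clock stops at | Method |
|---|---|---|---|
| Protocol 9.3 | Responders | Best response (CR, else PR) | not stated there |
| Protocol 9.7 | Responders only | by reference to 9.3 | Kaplan-Meier median, 95% CI |
| SAP section 6 | Responders | Best response (CR, else PR) | Median, 95% CI |
| SAP 8.2.3, as carried out | not stated | not stated | Quantitative summary under 8.1.1 |
| SAP 8.2.9 row | Full Analysis Set, no restriction | First response | Kaplan-Meier median, 95% CI |

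The 8.2.9 row alone names first response and alone lacks a responder restriction where a population is given. Two neighbouring rows in the table do restrict: duration of response in the analysis-set column, and swimmer plots in the method text.

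**2. Effect of the event date on one patient**

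Error = date of best response − date of first response. With PR at month 3 and CR at month 9, the row gives 3 months, section 6 gives 9, and the error is 9 − 3 = 6 months. When first response is also best response, the error is 0.

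**3. Effect of the event date across responders (assumed inputs)**

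Mean understatement = (share of responders with PR then CR) × (mean PR-to-CR gap).

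Assume first response at months 3, 6, 9, 12 with probabilities 0.50, 0.25, 0.15, 0.10, and PR-to-CR gaps of 3, 6 or 9 months, equally likely (mean 6).

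- Mean time to first response: 3×0.50 + 6×0.25 + 9×0.15 + 12×0.10 = 5.55 months.
- Share 0.10: 0.10 × 6 = 0.6, so the mean to best response is 6.15.
- Share 0.50: 0.50 × 6 = 3.0, so 8.55.
- Share 0.70: 0.70 × 6 = 4.2, so 9.75.
- Share 0: no difference.

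The median to best response in responders is 6, 9 and 9 months for shares 0.10, 0.50 and 0.70. The median to first response falls at 3 to 6 months, because exactly half of first responses are placed at month 3. The median gap is therefore sensitive to that choice, and the means are the steadier guide.

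**4. Effect of the population (assumed inputs)**

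Keep the first-response pattern above. Censor non-responders at progression (exponential, median 24 months) or at month 24. The SAP does not state this rule.

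Kaplan-Meier step: S(t) = S(previous) × (1 − events/at risk). For response rate 0.50, at risk at month t = responders still waiting + 0.50 × 2^(−t/24).

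- Month 3: 1 − 0.250/0.9585 = 0.739
- Month 6: 0.739 × (1 − 0.125/0.6704) = 0.601
- Month 9: 0.601 × (1 − 0.075/0.5106) = 0.513
- Month 12: 0.513 × (1 − 0.050/0.4036) = 0.449

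The full-set median is 12 months. The same steps leave S at 0.660 for a response rate of 0.30 and 0.501 for 0.45 after the last response, so the median is not reached. For 0.60, S falls to 0.424 at month 9, a median of 9 months.

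**5. Effect of the method**

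In responders only, every patient has the event and none is censored. The Kaplan-Meier median then essentially equals the sample median. What can differ is the interval: SAP 8.1.1 provides a 95% CI only for data judged normal, and otherwise gives the median and IQR.

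**The case against.** The strongest reply is that the table row does not govern.

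- The definition appears consistently in protocol 9.3, protocol 9.7 and SAP section 6, and section 6 says its endpoint list is meant to reflect the analyses conducted.
- SAP 8.2 notes that some proposed analyses were not conducted and remain as a record. The 8.2.9 table holds other outdated content, such as treatment patterns at 3 years although the analysis uses 2-year data.
- The analysis-set column is used loosely: the swimmer-plot row names the Full Analysis Set and then limits itself to responders.
- The row's wording on a first best overall response could mean the first date the best response was recorded.

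Much of this stands. It shows which definition is intended. It does not clear the row, which is not marked as superseded and goes on to name the date of first response as its end date. The account of the work done in 8.2.3 does not say which date or population was used.

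Three stronger readings are tempting, and the documents support none of them.

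- **Reported figures are wrong.** Nothing shows that the table was the programming source. 8.2.3 reports time to best and time to first response as two variables.
- **Non-responders are certainly included, so the median is not reached.** The SAP gives no censoring rule for patients who never respond, and the result moves with the assumptions: 12 months at a 50% response rate, 9 months at 60%.
- **Kaplan-Meier and the simple summary give conflicting medians.** In responders they essentially agree; only the interval is open.

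**Conclusion.** The row is wrong as written and should be corrected. It contradicts the SAP's own definition on event date and, by omission, on population.

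The direction of the event-date error is certain: too short for every patient with PR followed by CR, correct for all other responders. Its size in the cohort is not known. On the assumptions shown, the mean time in responders is understated by 0.6 to 4.2 months as the PR-then-CR share runs from 10% to 70%, and by nothing if that share is zero. The population effect is conditional on reading the analysis-set cell literally and on a censoring rule that the SAP does not contain.

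The endpoint is secondary in a descriptive study without a hypothesis, so the consequence is a mislabelled or ambiguous summary. No inference or sample size is affected.

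**What to change.** - In the 8.2.9 row, set the population to patients achieving CR or PR during follow-up, as the duration-of-response row does.
- Set the event date to the first date on which the best overall response (CR, or PR if no CR) is documented.
- Keep the median with 95% CI that section 6 promises, and reconcile it with the 8.1.1 summary described in 8.2.3 by naming one method for the interval.
- Give time to first response its own row.
- Check the program, and confirm that any figures already produced used the section 6 definition. Re-run them if they did not.

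The cost is a wording change to one table row, one added row, a sentence on the interval and a check of the program. No new data are needed.
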